
Study Design

Methods

Randomized Double-Blind Crossover Placebo controlled prospective trial

Sample

Inclusion Criteria: >18 years old, diagnosis of IEM, negative EGD or barium swallow, biopsies negative for EOE Exclusion Criteria: Have not had any changes to serotonin modulating medications over the last 6 weeks This is a cross-over style study and all participants will be both studied in the treatment and control arms.

NCT: 02674412

Version Date: 08/10/2016

Previous studies have shown up to a 100% improvement in baseline manometric findings in patients treated with buspirone. We hope to show at least a 25% difference with a p<0.05 and power 0.8. To show this effect, we will need 15-20 patients (depending on the standard deviation of the specific marker being tested).

Research Procedures – Define the data to be collected to answer the hypothesis/research question(s)

Nurses at the Swallowing Center facilitate the final read by a licensed physician of all manometries performed here. For every patient diagnosed with functional dysphagia and IEM who meets the inclusion and exclusion criteria, the nurses will notify the investigators. Review of electronic charts for all patients undergoing manometry is part of the routine medical practice and responsibility of the nurses. The nurses will also seek the patient's permission to be contacted to hear about the details of an ongoing study related to their diagnosis.

Once the investigators are notified of this diagnosis, one of the investigators will contact the patient to discuss the logistics of the study as well as obtain informed consent. After informed consent is obtained, patients will be randomized to either group A or group B. Both patients and investigators will be blinded to the assignment. All patients will be administered a Mayo Dysphagia Questionnaire as well as a validated GERD questionnaire. Subsequently, all patients in Group A will receive placebo and Group B will receive buspirone administered by pharmacy.

After two week of treatment, all patients will undergo repeat administration of questionnaires as well as assessment of side effects. They will also undergo repeat manometry. All participants will be reimbursed with \$100 for travel expenses.

Subsequently, all patients will be treatment free for a washout period of two weeks.

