Patients in Group A will then be treated with buspirone and Group B will be treated with placebo for two weeks followed by repeat questionnaires and manometry. All participants will be reimbursed with another \$100 for travel expenses.

All participants will be contacted by phone one week after they start their treatments to assess for tolerability and side effects related to the medication.

The two interventions that are part of the study are buspirone as well as the two subsequent manometries. Both costs will be incurred by the investigators.

Data Analysis

Descriptive statistics will be computed for all variables. This includes means, standard deviation and percentiles for continuous variables and frequencies and percentages for categorical factors the t test and odds ratio will be calculated for comparison. All analyses will be performed using SAS (version 9.2, The SAS Institute, Cary, NC). The analysis will be completed by one of the investigators.

Adverse Events and Data Monitoring Committee(DMC)

This project does not require an independent DMC or DSMB because this is an open-label intervention looking solely at symptom/sign changes related to buspirone.

After two weeks of being on the medication, each patient will be questioned about his/her baseline symptoms, new symptoms, and any side effects related to the medications (specifically the common side effects of buspirone). All Adverse Events will be reported to the IRB using the Adverse Event Form.

Consent

The consent interview will take place in private patient rooms at the Swallowing Center.

The consent interview will take place after patients are diagnosed with functional dysphagia or IEM. One of the investigators will discuss the study in detail and answer all questions. The patients will then be provided the opportunity to sign the consent or take time to think about the study before signing or rejecting the study.

The consent will be documented on the informed consent form attached with the application.

NCT: 02674412

Version Date: 08/10/2016

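### No questionnaire is given at the end of washout, so the plan cannot directly check whether symptoms returned to their starting level before period 2

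*Combined protocol and SAP*

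**What the plan says.** The Methods section describes a "Randomized Double-Blind Crossover Placebo controlled prospective trial". Group A takes placebo then buspirone, and Group B the reverse, for two weeks each.

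Under Research Procedures, before treatment starts, "All patients will be administered a Mayo Dysphagia Questionnaire as well as a validated GERD questionnaire". Both are repeated, with manometry, after the two weeks of period 1. Then "all patients will be treatment free for a washout period of two weeks". The second treatment is given "for two weeks followed by repeat questionnaires and manometry". No assessment is listed between the end of period 1 and the start of period-2 treatment.

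The other contacts do not fill the gap. The phone call one week into treatment covers tolerability and side effects. The questioning described in the adverse events section takes place after two weeks on medication.

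Data Analysis names a t test and an odds ratio. It mentions neither carryover nor period effects, nor how the entry scores will be used.

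**The concern.** A two-period crossover compares each patient with himself or herself, on the premise that period 2 starts from about the same state as period 1. The washout is there to secure this, but no symptom measurement shows whether it did.

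If some buspirone benefit is still present in Group B at the end of the placebo period, that placebo score is too good and the treatment effect is underestimated. A null or weak symptom result could then not readily be told apart from an incomplete washout. The stakes are real because dysphagia and GERD symptoms are two of the three outcomes that the Background expects buspirone to improve, and these questionnaires are how they are scored. The missing scores cannot be recovered once period 2 has begun.

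**Working it through.** **1. Schedule, from Research Procedures.**

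| Time | Group A / Group B | Questionnaires |
|---|---|---|
| Week 0, entry | untreated | yes |
| Week 2, end of period 1 | placebo / buspirone | yes |
| Week 4, end of washout | untreated | none listed |
| Week 6, end of period 2 | buspirone / placebo | yes |

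**2. Size of the bias.** Let τ be the buspirone effect, π the period effect and Lτ what persists in Group B at week 6. Assume equal group sizes, since no allocation ratio is stated. Buspirone minus placebo has expectation:
- Group A: τ + π
- Group B: τ − π − Lτ
- Average: τ(1 − L/2)

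At L = 0.2 this is 0.90τ, and at L = 0.5 it is 0.75τ. If a paired t test at n = 15 or 20 has 80% power for τ, power falls to about 71% and 56%.

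**3. The plan's own figure.** The plan seeks "at least a 25% difference with a p<0.05 and power 0.8" and states "To show this effect, we will need 15-20 patients", "depending on the standard deviation of the specific marker being tested". No standard deviation is given, so the figure can be neither reproduced nor refuted. Solving backwards (paired t test, two-sided 0.05, noncentral t), it fits an SD of the within-patient difference of 32.1 points at n = 15 and 37.9 at n = 20. The normal approximation, 25√n/(1.960 + 0.842), gives 34.6 and 39.9. The 25% target is set out for manometric findings and none is given for the questionnaires, so these values only provide a scale for the next step.

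**4. Can carryover be seen?** Assume a within-patient correlation r of 0.3 to 0.7. One score has SD s = SD_diff/√(2(1 − r)).
- Planned data: compare the sum of both period scores between sequences. SD of the sum = s√(2(1 + r)).
- With an end-of-washout score: compare it between sequences, adjusted for entry. Residual SD = s√(1 − r²).

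At n = 20 and r = 0.5, s = 37.9. The sum has SD 65.6 and standard error 65.6 × √(4/20) = 29.3. The adjusted washout score has SD 32.8 and standard error 14.7. Over n = 15-20 and r = 0.3-0.7, power is:

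| Carryover | Planned data | With washout score |
|---|---|---|
| 12.5 points | 6-8% | 12-14% |
| 25 points | 9-18% | 33-41% |

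The two columns concern different times: persistence at week 6 and at week 4 respectively. For the unadjusted end-of-washout minus entry change at n = 20 and r = 0.5, the 95% interval for the difference between sequences is about ±2.101 × 37.9 × √(4/20) = ±36 points.

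**5. Precision.** Take residual variance of the within-patient difference relative to no covariate. With four equally spaced scores and AR(1) correlation r between neighbours:
- Entry score as covariate: 1 − r²(1 − r²)/2
- Entry and end-of-washout scores as covariates: 1 − r²/(2(1 + r²))

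| r | Entry only | Both | Added gain (points) |
|---|---|---|---|
| 0.3 | 0.959 | 0.959 | 0.0 |
| 0.5 | 0.906 | 0.900 | 0.6 |
| 0.7 | 0.875 | 0.836 | 3.9 |
| 0.8 | 0.885 | 0.805 | 8.0 |

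Under equal correlation at all times, both gains are zero. A gain of 8 points is worth 0.08 × 20 = 1.6 patients, so at most 2 of 20. Adding a patient effect with a neighbour correlation near 0.9 can raise the gain to about 12 points. Change from each period's own baseline raises the variance 1.2- to 2.0-fold for r = 0.8 down to 0.3 under AR(1) and under equal correlation, so change scores should not be used.

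**6. Risk of adjusting for the washout score.** Suppose a fraction L of the effect remains in Group B at week 4 but is gone by week 6. The unadjusted contrast is then unbiased. Under AR(1), adjusting for the difference between the two baselines has slope r/2 and inflates the effect by rL/4: at L = 0.5, 6.25% for r = 0.5 and 8.75% for r = 0.7. With the two scores as separate covariates the slope on the washout score is −r³/(1 + r²). The inflation is then r³L/(2(1 + r²)), or 2.5% and 5.8%.

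**The case against.** The best defence is that the plan already deals with carryover by design, through a washout, and that the added score would do little. Its power for carryover is low. It also measures persistence two weeks after Group B's last buspirone, whereas the bias depends on persistence at four weeks. The only stated target effect is manometric. A more basic gap is that no paired or period-adjusted model is named. All of this stands, and it limits the point to an inexpensive descriptive check. It does not remove the gap: a premise of the design goes unmeasured although measuring it would be easy.

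Three stronger readings are tempting, and the documents do not support them.
- A reader might infer that carryover is present or that the washout is too short. The documents contain no data on persistence, and the length is not judged here.
- A reader might infer that carryover would be wholly invisible. A between-sequence comparison of period sums exists, and Group B's period-2 placebo scores can be set against Group A's period-1 placebo scores. These comparisons are weak and are confounded with sequence or period effects.
- A reader might infer that, without a second baseline, baseline data cannot improve precision, or might square an ordinary score correlation and claim that share of variance as the saving. The entry score cancels only when it is subtracted from both periods. As a covariate it can cut variance by up to 12.5% under AR(1). The saving from adjusting for the difference between baselines depends on the correlation between two differences, which is r/2 under AR(1) and zero under equal correlation.

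**Conclusion.** The point holds as a cheap improvement, not as an error that invalidates the design. The plan cannot directly check return to the starting symptom level before period 2. The possible cost is an underestimate of the symptom effect by L/2, with L unknown. An end-of-washout score would make the premise visible, but only descriptively at 15-20 patients.

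Precision is not a main reason for the change, because any gain beyond the entry score depends on a correlation pattern that the documents do not give. The bias formula rests on balanced sequences and on carryover in Group B only. The power figures rest on an SD solved back from the manometric sample-size statement and on assumed correlations of 0.3-0.7.

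**What to change.** - Repeat the Mayo Dysphagia Questionnaire and the GERD questionnaire at the end of washout, just before the first period-2 intake, by phone or at dispensing. No extra manometry is needed.
- Report the end-of-washout minus entry score by sequence with confidence intervals, as a description. State in advance that no carryover test will be used to discard period 2.
- Keep a within-patient treatment comparison, without the washout score, as the main symptom analysis, and say so in Data Analysis. A period term should be specified there too.
- An analysis with the entry and end-of-washout scores as covariates, not as change scores, may be added as a sensitivity analysis.

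The cost is two questionnaires per patient at one more time point. The downsides are slight patient burden, low power to detect carryover, and possible bias in the sensitivity analysis if carryover is present at the end of washout but gone by the end of period 2.

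### No safety questions are planned in the washout or after the last visit, so events after stopping buspirone go unsolicited in Group A and are first asked about on placebo in Group B

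*Combined protocol and SAP*

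**What the plan says.** The contact schedule is spread over Research Procedures and the section on adverse events and data monitoring.

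- Period 1: "all patients in Group A will receive placebo and Group B will receive buspirone administered by pharmacy". At its end, "After two week of treatment, all patients will undergo repeat administration of questionnaires as well as assessment of side effects", together with a repeat manometry.
- Washout: "Subsequently, all patients will be treatment free for a washout period of two weeks". No contact is described in this interval.
- Period 2: Group A crosses to buspirone, and "Group B will be treated with placebo for two weeks followed by repeat questionnaires and manometry". No later contact is described.
- Phone call: "All participants will be contacted by phone one week after they start their treatments", to ask about tolerability and drug-related side effects.
- Adverse-event section: "After two weeks of being on the medication, each patient will be questioned about his/her baseline symptoms, new symptoms", and about side effects.

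The adverse-event section also sends every adverse event to the IRB on a standard form, but sets no collection window and no rule for events that begin off treatment. Research Procedures counts the manometries among the study's interventions: "The two interventions that are part of the study are buspirone as well as the two subsequent manometries".

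**The concern.** In a crossover, each treatment's harms should be looked for in the same way whichever sequence the patient draws. Here, what happens after buspirone is stopped is asked about late and during placebo in one sequence, and is not asked about in the other. The week-5 call asks about effects of the medication. For Group B the treatment then being taken is placebo, so a washout event could be passed over or recorded under the wrong treatment. Data Analysis plans an odds ratio for categorical variables; if side effects are among them, a misplaced event would reach the reported comparison.

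The protocol also dispenses with an independent monitoring committee, so scheduled questioning is the only active safety surveillance it describes. An event in the unasked intervals reaches the IRB only if the patient raises it. The same holds for anything that follows the second manometry.

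**Working it through.** The plan gives no figure of its own on this point, so there is none to reproduce. The check is arithmetic on the schedule, followed by a formula for the possible effect on event rates.

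**Timeline.** Inputs from Research Procedures: two weeks of treatment, two weeks of washout, two weeks of treatment, and a call one week after the start of treatment. With week 0 as the start:

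- period 1 is weeks 0–2, washout is weeks 2–4, and period 2 is weeks 4–6;
- calls fall at 0 + 1 = week 1 and 4 + 1 = week 5;
- visit questioning falls at week 2 and week 6.

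Safety contacts are therefore at weeks 1, 2, 5 and 6. None falls between week 2 and week 5, or after week 6.

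| | After buspirone | After placebo |
|---|---|---|
| Group A (placebo, then buspirone) | stops week 6; no later contact | stops week 2; next asked week 5, on buspirone |
| Group B (buspirone, then placebo) | stops week 2; next asked week 5, on placebo | stops week 6; no later contact |

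The Group B gap after buspirone is 5 − 2 = 3 weeks, or 21 days. It runs from stopping the drug. An event in the washout (weeks 2–4) would be between 5 − 4 = 1 and 5 − 2 = 3 weeks old at the call.

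**Other readings of the text.** The schedule above favours the protocol.

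- If the call is made only once, in period 1, Group B is next asked at week 6, a gap of 6 − 2 = 4 weeks.
- If, in addition, the adverse-event section's questioning applies only after buspirone, Group B is not asked again.
- The period 2 text lists questionnaires and manometry only, so the week-6 safety questions rest on the general sentence in the adverse-event section.

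No reading adds a contact in washout or after week 6.

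**Patients without contact after buspirone.** With equal allocation (assumed; no ratio is stated), Group A is half of 15–20 patients: 7 or 8 of 15, or 10 of 20.

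**Possible effect on event rates.** Let qB and qP be the probabilities of a washout event after buspirone and after placebo. Assume equal allocation, that every washout event is elicited at week 5 and charged to the treatment then being taken, and that the patient has no event already counted under that treatment.

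- Added to the placebo rate, from Group B: qB × 1/2.
- Added to the buspirone rate, from Group A: qP × 1/2.
- Shift in buspirone minus placebo: (qP − qB)/2.

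| Assumed qB | Assumed qP | Shift |
|---|---|---|
| 10% | 10% | 0 points |
| 20% | 20% | 0 points |
| 20% | 10% | (10 − 20)/2 = −5 points |
| 20% | 0% | (0 − 20)/2 = −10 points |

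A negative shift moves the comparison towards no difference when buspirone has the higher event rate. All these rates are illustrative; the documents give none.

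**The case against.** The strongest reply is that the design is symmetric. Group A passes through the same unasked washout after placebo, and its events would surface on buspirone. Likewise, the missing contact after week 6 loses solicited follow-up after buspirone in Group A and after placebo in Group B. This stands. A reader might infer that the plan biases tolerability towards no difference by a set amount, such as 10 points at a 20% event rate. That holds only if no washout event ever follows placebo, which nothing in the documents supports.

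A reader might also infer that events after buspirone are lost. The documents show only that they are not actively sought. All adverse events are to go to the IRB, unprompted reports are not excluded, and the consent form, which might tell patients to report problems between visits, is not available for this review.

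A third tempting reading is that effects of manometry are never asked about. The adverse-event section does ask about new symptoms, so symptoms from the first manometry could be raised later. What remains is that no contact follows the final one.

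Finally, the stated hypothesis concerns motility, dysphagia and GERD, and no tolerability endpoint is named. That limits the weight of the point but does not remove it: the protocol undertakes to assess side effects in both treatments, and its schedule does so unevenly after treatment stops.

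**Conclusion.** The gap in planned safety questioning is real on every reading of the schedule. On the most favourable one, Group A has no planned safety contact after stopping buspirone, Group B waits 21 days and is then already on placebo, and no contact follows the last manometry.

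The direction and size of any bias in the tolerability comparison are not established. Under the attribution assumptions set out above, the shift depends on the difference between two rates that the documents do not give. No fixed figure should be claimed. The firm conclusion is unequal ascertainment between sequences, with no onset date or attribution rule to repair it afterwards. The efficacy comparison is unaffected. This is a change that should be made for safety detection and fair reporting of side effects; it is not a threat to the trial's main result.

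**What to change.** Ask the existing new-symptom and side-effect questions at two further points: at the end of washout before period 2 starts, and by one phone call two weeks after period 2 ends. Both sequences then have two weeks of solicited follow-up after each treatment. Word the questions to include symptoms after manometry. Record an onset date for every event, and tabulate events that begin off treatment in separate rows by the preceding treatment, not under the next one.

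The cost is one or two short contacts per patient, the lower figure if the washout questions can be joined to a contact that takes place anyway. That is 15 × 1 = 15 to 20 × 2 = 40 contacts in total. It also needs one onset-date field and two more weeks before each patient's record closes. No new procedure is needed, and treatment is unchanged.

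### The only comparative analysis named for this two-period crossover is a t test and an odds ratio; pairing, matching and period are left unspecified

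*Combined protocol and SAP*

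**What the plan says.** The Sample section says "This is a cross-over style study and all participants will be both studied in the treatment and control arms". Under Research Procedures, "patients will be randomized to either group A or group B". In the first period "all patients in Group A will receive placebo and Group B will receive buspirone administered by pharmacy". Then "all patients will be treatment free for a washout period of two weeks", after which the treatments are exchanged: "Patients in Group A will then be treated with buspirone and Group B will be treated with placebo for two weeks". Manometry and questionnaires follow each period. This is a standard two-sequence, two-period crossover.

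After the descriptive statistics, the Data Analysis section gives one comparative clause: "the t test and odds ratio will be calculated for comparison". The Sample section sizes the trial for a 25% difference with p<0.05 and power 0.8, and says "we will need 15-20 patients (depending on the standard deviation of the specific marker being tested". No SD, within-patient correlation, sidedness or type of t test is given. Pairing, matching, patient, period and sequence do not appear anywhere as parts of the analysis.

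**The concern.** Each patient contributes two correlated results, one per period, and treatment order differs between groups. The analysis should use the pairing, and it can remove any general shift between the first and second period. The plan commits to neither, so the choice falls to the investigator who runs the analysis.

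Three readings are possible, each with its own consequence:

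- **Paired t test.** It uses the pairing but omits period. A period shift goes into the error term and, if the sequences are unequal in size, into the estimate.
- **Unpaired t test.** It ignores the correlation and so uses too large a standard error.
- **Ordinary 2x2 odds ratio.** It counts two answers from one patient as two independent patients. Side effects are the only yes/no data that the plan clearly names ("all patients will undergo repeat administration of questionnaires as well as assessment of side effects").

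**Working it through.** **Inputs.** From the Sample section: n = 15 to 20, a 25% difference, alpha 0.05 (taken as two-sided), power 0.80. Period effects (0.2 and 0.5 SD of the within-patient difference) and correlations (rho 0.3, 0.5, 0.7) are assumptions, because the documents give none.

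**1. The plan's own sample size.** It cannot be reproduced without an SD, so I solved for the SD that gives 80% power, using the noncentral t distribution.

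| Test | SD at n=15 | SD at n=20 |
|---|---|---|
| Paired t, n-1 df (SD of the difference) | 25/0.778 = 32.1% | 25/0.660 = 37.9% |
| Crossover with period term, n-2 df (SD of the difference) | 25/0.783 = 31.9% | 25/0.662 = 37.7% |
| Unpaired t, n results per condition (SD per condition) | 23.6% | 27.5% |

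All three SDs are possible, so the stated n does not show which test was meant.

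**2. Paired t without period.** Write each patient's buspirone-minus-placebo difference as D = treatment effect + p in one sequence and treatment effect - p in the other, plus noise with SD 1. Here p is the period effect in SDs of the difference.

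- Bias = (n1 - n2)/n x p. It is zero for equal sequences and p/3 for a 2:1 split. At n=15 split 10:5, with SD 32.1%, that is 0.2 x 32.1/3 = 2.1 or 0.5 x 32.1/3 = 5.4 percentage points, against the 25% target.
- Standard error inflation with equal sequences = sqrt(1 + p² x n/(n-1)). At n=20: sqrt(1 + 0.04 x 20/19) = 1.02 and sqrt(1 + 0.25 x 20/19) = 1.12.

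Simulated results (200,000 replicates; effect sized for 80% paired power):

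| Split | Quantity | p = 0.2 | p = 0.5 |
|---|---|---|---|
| 8:8, 10:10 | Power, no period term | 79% | 72% |
| 8:8, 10:10 | Power, period-adjusted | about 80% | about 80% |
| 8:8, 10:10 | Type I error, no period term | 4.5-4.6% | 2.9-3.0% |
| 10:5, 12:6 | Type I error, no period term | 5.3-5.4% | 6.3-7.0% |

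At 9:6 and 12:8, type I error does not exceed 5%. The period-adjusted analysis holds about 5.0% throughout.

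**3. Chance of a 2:1 or worse split.** Under simple randomisation this is 2 x P(Binomial(n, 1/2) ≥ 2n/3): 30% at n=15 (10 or more in one group), 24% at n=18 (12 or more) and 12% at n=20 (14 or more). Averaged over all splits, type I error is 5.0-5.1%.

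**4. Baseline.** For a change from one pre-treatment value B, (Y_buspirone - B) - (Y_placebo - B) = Y_buspirone - Y_placebo. The baseline cancels, so it does not adjust for period.

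**5. Unpaired t in a trial sized for a paired test.** Its standard error is too large by 1/sqrt(1 - rho): 1.20, 1.41 and 1.83 at rho 0.3, 0.5 and 0.7. Simulated power is 70-71%, 54-56% and 26-28%; type I error is about 2.1%, 0.8% and 0.1%.

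**6. Exact McNemar.** With m discordant patients the smallest two-sided p is 2 x (1/2)^m: 0.0625 at m=5 and 0.031 at m=6. Significance at 0.05 therefore needs at least 6.

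**The case against.** The strongest reply is that the plan does not exclude pairing. Every patient is studied on both treatments, and a statistician would read the t test as paired. In a near-balanced crossover that test is valid and slightly conservative without a period term. Nothing in the documents points to a period effect, and at 0.2 SD the loss is one point of power. All of this stands, and it limits the size of the point.

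The two-week washout is a weaker reply. It addresses carryover, not a shift between periods, and a period term in turn does not solve carryover.

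A reader might infer that the plan prescribes an unpaired analysis, and so that power falls to the figures in step 5. The text is silent on pairing, so those figures describe an outcome that is only left open. A reader might also infer that false positives are generally inflated. They are not: the excess is conditional on a split near 2:1 or worse together with a real period effect, and the split probabilities assume simple randomisation, which the documents do not state.

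Nor should the baseline be called pre-randomisation throughout. Research Procedures lists the questionnaires after randomisation and before treatment; only the diagnostic manometry clearly comes earlier. The cancellation in step 4 holds either way.

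**Conclusion.** The point holds as a gap in specification: the plan names neither pairing, matching nor period for a design that calls for all three. On the natural paired reading the cost is modest. It ranges from about one point of power (period effect 0.2 SD) to about eight points (0.5 SD) with equal sequences. With unequal sequences there is a bias of (n1 - n2)/n times the period effect. These sizes rest on assumed period effects. The remaining risk is that the text also permits an unpaired t test, which loses power when the two results from a patient are positively correlated, and an ordinary odds ratio, whose independence assumption the design contradicts. This is a cheap improvement; the documents do not support calling the planned comparison invalid.

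**What to change.** Replace the comparative clause in Data Analysis with:

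> Continuous outcomes: linear mixed model (SAS PROC MIXED) with treatment, period and sequence as fixed effects and patient as random effect, reporting buspirone minus placebo with 95% CI. Binary outcomes: discordant-pair counts and the exact McNemar test; no ordinary 2x2 odds ratio is used for inference.

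Optionally, randomise the A/B sequence in permuted blocks. With period in the model, an unequal split no longer biases the estimate, so blocking serves only to keep the adjusted analysis efficient. Dropout can still unbalance the patients analysed.

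**Cost.** A change of wording and a few lines of SAS, with no new data. The period term takes one degree of freedom. With no period effect, power goes from 80.0% to 79.4-79.8% for near-balanced sequences, but to about 75% at a 2:1 split. The McNemar test has no period term and cannot reach p<0.05 with fewer than 6 discordant patients, so rare side effects will in practice be described rather than tested.

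### The odds ratio is the only comparison named that suits categorical outcomes; as named it does not use the pairing, and for side effects rare on placebo it will often have no finite value at 15-20 patients

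*Combined protocol and SAP*

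**What the plan says.** Data Analysis plans descriptive summaries of every variable, with counts and percentages for categorical ones. For comparison it names two methods: "the t test and odds ratio will be calculated for comparison". It mentions no risk difference, McNemar test, exact method or rule for zero cells.

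The design is a two-period crossover in which "all participants will be both studied in the treatment and control arms", so each patient supplies one observation on buspirone and one on placebo. The Sample section says "we will need 15-20 patients (depending on the standard deviation of the specific marker being tested"), so the size was set on manometric markers and not on side effects.

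Side effects are asked about by telephone one week into treatment. The adverse events section adds questioning after two weeks about "any side effects related to the medications (specifically the common side effects of buspirone"). The documents give no expected side-effect rate for either treatment. They also do not list the categorical variables to which the odds ratio will be applied.

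**The concern.** The t test does not serve yes/no data, so a categorical comparison made under this plan falls to the odds ratio. Two weaknesses follow.

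- **Pairing.** The same patients are observed on both treatments. An ordinary odds ratio treats the two sets of observations as independent groups, and the plan does not say that a matched version will be used.
- **Zero cells.** If no patient has a given side effect on placebo, the odds ratio is infinite, or undefined if there are also no events on buspirone. An infinite estimate is the same for 2 of 20 against none and for 8 of 20 against none, so it does not show how large the excess is. This pattern, with events on the drug and none on placebo, is the one a tolerability comparison most needs to describe.

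If no rule is set in advance, the way round a zero cell will be chosen after the data are seen.

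**Working it through.** **Inputs from the documents.** 15-20 patients, each observed on both treatments (Sample). Comparison methods: t test and odds ratio only (Data Analysis). Target: "We hope to show at least a 25% difference with a p<0.05 and power 0.8" (Sample).

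**Assumed inputs.** Placebo rate p0 of 2%, 5%, 10% or 20%. Buspirone rate p1 of 20% for the matched calculation. Events independent within patient between periods.

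**The plan's own figure.** The 15-20 patients cannot be reproduced, because no standard deviation is given. Solving backwards with a two-sided paired t test at 0.05 and power 0.8, a 25% difference needs 15 patients if the SD of the within-patient difference is about 32% of baseline, and 20 if it is about 38%. The range is therefore plausible for a manometric marker. It says nothing about side effects.

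**Step 1: ordinary odds ratio.** It has no finite value when there are no placebo events, which has probability (1 - p0)^n whatever the buspirone rate.

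| p0 | n = 15 | n = 20 |
|---|---|---|
| 2% | 0.98^15 = 74% | 0.98^20 = 67% |
| 5% | 0.95^15 = 46% | 0.95^20 = 36% |
| 10% | 0.90^15 = 21% | 0.90^20 = 12% |
| 20% | 0.80^15 = 3.5% | 0.80^20 = 1.2% |

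With p0 = 5% and p1 = 20%, nearly all of this is an infinite value (45% and 35%). The undefined case, with no events on either treatment, accounts for 1.6% and 0.4%.

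**Step 2: matched odds ratio.** This is the number of patients with the event on buspirone only divided by the number with it on placebo only. It has no finite value when nobody has the event on placebo only, which has probability (1 - p0(1 - p1))^n. With p1 = 20%:

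| p0 | n = 15 | n = 20 |
|---|---|---|
| 2% | 0.984^15 = 79% | 0.984^20 = 72% |
| 5% | 0.96^15 = 54% | 0.96^20 = 44% |

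Matching respects the design but does not remove the zero-cell problem.

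**Step 3: alternatives on the same data.** Take 20 patients, 3 with the event on buspirone only and none with it on placebo.

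- Odds ratio: infinite.
- Odds ratio with 0.5 added to each cell, ignoring pairing: 8.2, 95% CI 0.40 to 170.
- Paired risk difference: 3/20 - 0/20 = 15 percentage points, with a score (Tango) 95% CI of about -4 to 36.
- Exact McNemar: 2 × 0.5^3, p = 0.25.

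With no discordant patients among 20, the paired score interval is still finite: 0, with limits of about -16 to 16 points.

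**The case against.** A reader might infer that the tolerability comparison may yield nothing usable. The documents do not support that. Data Analysis also plans counts and percentages for categorical variables, so 3 of 20 against 0 of 20 would appear as 15% and 0%, and the difference is a subtraction.

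An infinite odds ratio is also not empty. With k buspirone-only patients and no placebo-only patients, the exact matched 95% lower limit is 0.025^(1/k) / (1 - 0.025^(1/k)). This is 1.18 for k = 6, which points to an excess on buspirone, and 0.41 for k = 3, which is inconclusive. The plan names no exact method, but the information can be recovered. For the same reason, a rule to show the odds ratio only where it is finite would be wrong: it would hide the result when events occur only on buspirone.

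Three further points stand.

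- Use of the odds ratio for side effects is inferred. A between-treatment comparison of side effects is itself only implied: the account of the second period lists questionnaires and manometry but does not repeat the side-effect assessment.
- The word *often* depends on assumed rates. Patients are asked directly about side effects, so low placebo rates cannot be taken for granted, and at 20% the unmatched problem nearly disappears.
- The alternative does not create precision. With no placebo-only patients, exact McNemar needs 6 buspirone-only patients for two-sided p < 0.05 (2 × 0.5^6 = 0.031). At 20% against 5%, the expected number of buspirone-only patients is 15 × 0.20 × 0.95 = 2.9 to 20 × 0.20 × 0.95 = 3.8.

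These points limit the harm. They do not make the odds ratio a good main measure for paired yes/no outcomes in so few patients.

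**Conclusion.** The point holds as a cheap improvement to a secondary comparison. For a side effect with an assumed placebo rate of 2-5%, the odds ratio has no finite value in about 36-74% of trials of this size, or 44-79% if matched with 20% on buspirone. At 10% on placebo the unmatched figure is 12-21%, and at 20% it is 1.2-3.5%. All these rates are assumptions. The matched figures also assume independence within patient; positive correlation would make placebo-only events rarer and raise them.

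What is lost is a finite, paired comparative estimate with a two-sided interval. The raw tolerability contrast is not lost. Conclusions on continuous measures such as the manometric markers do not depend on this point.

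**What to change.** In Data Analysis, make the paired risk difference the main comparison for categorical outcomes: the proportion on buspirone minus the proportion on placebo in the same patients. Give it a score-type 95% confidence interval for paired proportions and an exact McNemar p-value. If the odds ratio is kept, specify the matched one with exact limits, and report the lower limit when the estimate is infinite.

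This takes a sentence or two of text and slight extra analysis work. It needs no new data or patients. The intervals will be wide at 15-20 patients, and the report should say so.
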